### 10.1 Discontinuation of Study Product

A subject may be discontinued from the study product at any time whilst still in the study at the discretion of the investigator related to safety, subject consent or a potential worsening of the risk / benefit assessment from the subject of remaining on the intervention for the following reasons:

- Adverse Event
- Lack of efficacy from the intervention
- Subject request
- Subject to be withdrawn from the study (see Section [10.1.1](#))

#### 10.1.1 Subject Discontinuation/Withdrawal

A subject may withdraw from the study at any time at his or her own request or may be withdrawn at any time at the discretion of the investigator or sponsor for safety, behavioral reasons, or the inability of the subject to comply with the protocol-required schedule of study visits or procedures.

Inclusion/Exclusion criteria are assessed at Baseline. Any participant who develops exclusionary symptoms during the course of the trial can be withdrawn at the discretion of the investigator.

The following circumstances require discontinuation of study product and/or premature subject withdrawal:

- Protocol violation that may impact the subject's safety
- Withdrawal of informed consent
- Subject lost to follow-up
- Unblinding of the subject
- Pregnancy
- Investigator withdrawal due to worsening severity of health condition

If the subject withdraws from the study and withdraws consent for disclosure of future information, no further evaluations should be performed, and no additional data should be collected. The sponsor may retain and continue to use any data collected before such withdrawal of consent.

### **10.1.2 Lost to Follow up**

If a subject fails to complete two consecutive days of e-diaries, the investigator or designee must make every effort to regain contact with the subject (where possible, 3 telephone calls or emails or local equivalent methods) and counsel the subject on the importance of maintaining the assigned activity schedule and ascertain whether the subject wishes to and/or should continue in the study.

A subject will be considered lost to follow up and withdrawn from the study if he or she repeatedly fails to complete scheduled activities and is unable to be contacted following the 3 contact attempts by the study team.

If contact is made with the subject, the investigator should inquire about the reason for withdrawal and if appropriate request that the subject attend a final virtual visit and follow-up with the subject regarding any unresolved adverse events (AEs).

## **11 DATA MANAGEMENT**

### **11.1 Case Report Form**

An eCRF is an electronic document designed to record the protocol required information to be reported to the sponsor on each trial subject.

For each subject who has given informed consent the eCRF must be completed and signed by the Principal Investigator (or authorized designee) to certify that the data are complete and correct. The investigator must maintain accurate documentation (source data) that supports the information entered in the eCRF.

### **11.2 Data Handling**

Documentation of all data management activities should allow step-by-step retrospective assessment of data quality and study performance.

Any changes or corrections to data will be performed in the Electronic Data Capture (EDC) System, and it will include rationale for changes. The EDC system has an audit trail, which will provide a complete record of the changes and corrections endorsed by the Investigator.

Adverse events will be coded using Medical Dictionary for Regulatory Activities (MedDRA) and any concomitant medications terms (if applicable) using an internal validated medication dictionary. The MedDRA dictionary version will be documented within the Data Management Plan (DMP).

### **11.2.1 Data Queries**

Programmed edit checks will be generated automatically, as the data are being entered into the system. Reports and listings on the CRF data will also be run, in addition to the queries already programmed and generated by the system, to raise manual queries as needed for site clarification or correction. The Clinical Dictionary Development and Management Group will raise queries as needed on safety data to code the terms (AEs and Drugs or concomitant medication) appropriately.

The study monitor will perform ongoing review of the CRFs in accordance with the monitoring plan, to confirm that data entered into the CRF by authorized site personnel are accurate and complete; that the safety and rights of participants are being protected; and that the study is being conducted in accordance with the currently approved protocol and any other study agreements, ICH GCP, and all applicable regulatory requirements.

Any queries will be generated in the EDC System to the Investigator or designee, enabling the errors to be addressed in parallel with Data Management review. The study monitor can also run reports and listings on the CRFs, to raise manual queries as needed for site clarification or correction.

## **11.3 Processing Patient Reported Outcomes and Data Collection from Internet of Medical Things**

Electronic Patient reported outcome (ePRO) that are measured by Internet of Medical Things (IoMT) devices (i.e., wearables, patches, sensors, and mobile data collection units such as smartphones and tablets) will be transferred in the protocol-specified aggregated and/or raw form electronically to Haleon or Third-party data management vendor.

All ePRO source data should be reviewed by the study staff and the study monitor to ensure accurate transcription of data and that any potential AEs or concomitant medications reported on these documents are discussed with the subject and transcribed accurately to the eCRF and/or DMS. ePROs that are classed as source data will be retained by the investigator and true/certified copies may be sent to a designated vendor or Haleon as required. Any AEs or concomitant medications collected as ePRO will be reviewed and transcribed to the eCRF by the site.

To protect the privacy of subjects, no Personal Information (PI) (including the subject's name or initials or birth date) is to be recorded on any PRO/ePRO/IoMT Devices Data that will be forwarded to Haleon or Third-Party Vendor.

## 12 STUDY GOVERNANCE CONSIDERATIONS

Electronic Patient reported outcome (ePRO) that are measured by Internet of Medical Things (IoMT) devices (i.e., wearables, patches, sensors, and mobile data collection units such as smartphones and tablets) will be transferred in the protocol-specified aggregated and/or raw form electronically to Haleon or Third-party DM vendor.

All ePRO source data should be reviewed by the study staff and the study monitor to ensure accurate transcription of data and that any potential AEs or concomitant medications reported on these documents are discussed with the subject and transcribed accurately to the eCRF and/or DMS. ePROs that are classed as source data will be retained by the investigator and true/certified copies may be sent to a designated vendor or Haleon as required. Any AEs or concomitant medications collected as ePRO will be reviewed and transcribed to the eCRF by the site.

To protect the privacy of subjects, no Personal Information (PI) (including the subject's name or initials or birth date) is to be recorded on any PRO/ePRO/IoMT Devices Data that will be forwarded to Haleon or Third-Party Vendor.

### 12.1 Quality Control

When reviewing data collection procedures, the discussion will include identification, agreement, and documentation of data items for which the eCRF will serve as the source document.

**CCI** will monitor the study data to verify that the:

- Data are authentic, accurate, and complete.
- Safety and rights of subjects are being protected.
- Study is conducted in accordance with the currently approved protocol and any other study agreements, GCP, and all applicable regulatory requirements.

### 12.2 Quality Assurance

To ensure compliance with GCP and all applicable regulatory requirements, Haleon may conduct a quality assurance assessment and/or audit of the site records, and the regulatory agencies may conduct a regulatory inspection at any time during or after completion of the study.

In the event of an assessment, audit, or inspection, **CCI** must agree to grant the advisor(s), auditor(s), and inspector(s) direct access to all relevant documents and to allocate their time and the time of their staff to discuss the conduct of the study, any findings/relevant issues and to implement any corrective and/or preventative actions to address any findings/issues identified.

**CCI** will notify Haleon or its agents immediately of any regulatory inspection notification in relation to the study. The sponsor will be available to help **CCI** prepare for an inspection.

## **12.3 Regulatory and Ethical Considerations**

## **12.4 Institutional Review Board/ Ethics Committee**

It is the responsibility of the investigator to have prospective approval of the study protocol, protocol amendments, informed consent document, safety statement (including any updates) and other relevant documents, e.g. recruitment advertisements, if applicable, from the IRB/EC. All correspondence with the IRB/EC should be retained in the investigator file. Copies of IRB/EC approvals should be forwarded to Haleon prior to the initiation of the study, and also when subsequent amendments to the protocol are made.

The only circumstance in which an amendment may be initiated prior to IRB/EC approval is where the change is necessary to eliminate apparent immediate hazards to the subjects. In that event, the investigator must notify the IRB/EC and Haleon in writing immediately after the implementation.

## **12.5 Ethical Conduct of the Study**

The study will be conducted in accordance with the protocol and legal and regulatory requirements, as well as the general principles set forth in the International Ethical Guidelines for Biomedical Research Involving Human Subjects (Council for International Organizations of Medical Sciences 2002), International Ethical Guidelines for Health-Related Research Involving Humans (Council for International Organizations of Medical Sciences, 2016), guidelines for GCP (ICH 1996 and revision 2), and the ethical principles that have their origin in the Declaration of Helsinki (World Medical Association 2013).

In addition, the study will be conducted in accordance with the protocol, the ICH guideline on GCP, and applicable local regulatory requirements and laws.

## **12.6 Subject Information and Consent**

All parties will ensure protection of subject personal data and will not include subject names or other identifiable data in any reports, publications, or other disclosures, except where required by laws.

When study data are compiled for transfer to Haleon and other authorized parties, subject names, addresses, and other identifiable data will be replaced by numerical codes based on a numbering system provided by Haleon in order to de-identify study subjects.

The study site will maintain a confidential list of subjects who participated in the study, linking each subject's numerical code to his or her actual identity. In case of data transfer, Haleon will maintain high standards of confidentiality and protection of subjects' personal data consistent with applicable privacy laws.

## **12.7 Subject Recruitment**

Advertisements approved by IRBs and investigator databases may be used as recruitment procedures. Use of an IRB approved, generic, prescreening questionnaire to assess basic subject characteristics to determine general eligibility for this study is allowed.

Haleon will have an opportunity to review and approve the content of any study recruitment materials directed to potential study subjects before such materials are used.

## **12.8 Reporting of Safety Issues and Serious Breaches of the Protocol or ICH GCP**

Within Haleon a serious breach is defined as a breach likely to affect to a significant degree the safety and rights of a subject or the reliability and robustness of the data generated in Haleon sponsored human subject research studies.

In the event of any prohibition or restriction imposed (i.e., clinical hold) by an applicable competent authority in any area of the world, or if CCI is aware of any new information that might influence the evaluation of the benefits and risks of the investigational product, Haleon should be informed immediately.

In addition, CCI will inform Haleon immediately of any urgent safety measures taken by the investigator/designee to protect the study subjects against any immediate hazard, and of any serious breaches of this protocol or of ICH GCP that the investigator/designee becomes aware of.

## **12.9 Oversight Committees**

Due to the low-risk nature of the trial, no oversight committees will be utilized. Monitoring will occur as per the study-specific risk-based monitoring plan.

## **12.10 Disclosure and Publication Policy**

Study information from this protocol may be posted on publicly available clinical trial registers before enrollment of subjects begins in accordance with applicable Haleon policies.

Haleon intends to make anonymized subject-level data from this study available to external researchers for scientific analyses or to conduct further research that can help advance medical science. This helps ensure the data provided by study participants are used to maximum effect in the creation of knowledge and understanding.

The procedures and timing for public disclosure of the results summary and for development of a manuscript for publication will be in accordance with sponsor policy and as per the country specific requirements for disclosure.

## **12.11 Provision of Study Results to Investigators**

Where required by applicable regulatory requirements, a local PI signatory will be identified for the approval of the clinical study report. The local PI will be provided reasonable access to statistical tables, figures, and relevant reports and will have the opportunity to review the complete study results at a Haleon site or other mutually agreeable location.

Haleon will also provide the local PI with the full summary of the study results. The local PI is encouraged to share the summary results with the study subjects, as appropriate.

The procedures and timing for public disclosure of the results summary and for development of a manuscript for publication will be in accordance with Haleon Policy.

A manuscript will be progressed for publication in the scientific literature if the results provide important scientific or medical knowledge.

## 12.12 Records Retention

Following closure of the study, the investigator must maintain all site study records (except for those required by local regulations to be maintained elsewhere), in a safe and secure location.

Where permitted by local laws/regulations or institutional policy, some or all of these records can be maintained in a format other than hard copy (e.g., microfiche, scanned, electronic); however, caution needs to be exercised before such action is taken.

The investigator must notify Haleon of any changes in the archival arrangements, including, but not limited to, archival at an off-site facility or transfer of ownership of the records in the event the investigator is no longer associated with the site.

## 12.13 Conditions for Terminating the Study

Premature termination of this study may occur because of a regulatory authority decision, change in opinion of the IRB, or study product safety problems, or at the discretion of Haleon.

If a study is prematurely terminated, Haleon will promptly notify CCI [REDACTED]. After notification, CCI [REDACTED] must promptly contact all participating subjects and should assure appropriate therapy/ follow-up for the subjects. As directed by Haleon, all study materials must be collected and all eCRF's completed to the greatest extent possible. Where required by the applicable regulatory requirements, Haleon should inform the regulatory authority(ies) and the investigator should promptly inform the IRB and provide the IRB a detailed written explanation of the termination or suspension.

If the IRB terminates or suspends its approval/favorable opinion of a trial, the local PI or designee should promptly notify the Haleon and provide Haleon with a detailed written explanation of the termination or suspension.

Upon completion or premature discontinuation of the study, the Haleon monitor will conduct site closure activities with CCI [REDACTED] as appropriate, in accordance with applicable regulations including GCP, and Haleon Standard Operating Procedures.

14 APPENDICES

14.1 Schedule of Assessments Schematic

[figure not shown]
Pre-screening, Screening & Baseline (continues on next page)

[figure not shown]
## Screening & Baseline (continued from previous page, continues on next page)

[figure not shown]
## Screening & Baseline (continued from previous page), Active Trial (continues on next page)

Active Trial (continued from previous page), Active Trial (continues on next page)

## Active Trial (continued from previous page), End of Study

## 14.2 Study Assessments

### 14.2.1 Wisconsin Upper Respiratory Symptom Survey-21 (WURSS-21)

**Wisconsin Upper Respiratory Symptom Survey – 21 --- Daily Symptom Report**

Day:	Date:	Time:	ID:
------	-------	-------	-----

Please fill in one circle for each of the following items:

	Not sick 0	Very mildly 1	Mildly 2	Moderately 3	Moderately 4	Severely 5	Severely 6	Severely 7
How sick do you feel today?								

Please rate the average severity of your cold symptoms over the last 24 hours for each symptom:

	Do not have this symptom 0	Very mild 1	Mild 2	Mild 3	Moderate 4	Moderate 5	Severe 6	Severe 7
Runny nose								
Plugged nose								
Sneezing								
Sore throat								
Scratchy throat								
Cough								
Hoarseness								
Head congestion								
Chest congestion								
Feeling tired								

Over the last 24 hours, how much has your cold interfered with your ability to:

	Not at all 0	Very mildly 1	Mildly 2	Mildly 3	Moderately 4	Moderately 5	Severely 6	Severely 7
Think clearly								
Sleep well								
Breathe easily								
Walk, climb stairs, exercise								
Accomplish daily activities								
Work outside the home								
Work inside the home								
Interact with others								
Live your personal life								

Compared to yesterday, I feel that my cold is...

[figure not shown]
Very much better	Somewhat better	A little better	The same	A little worse	Somewhat worse	Very much worse
						

WURSS -21\* (Wisconsin Upper Respiratory Symptom Survey) 2004  
Created by Bruce Barrett MD PhD et al., UW Department of Family Medicine, [name]

### 14.2.2 Specific Quality of Life (QoL) Questions

#### 14.2.2.1 Baseline Questions (pre-treatment):

[figure not shown]
Please complete this questionnaire prior to your first dose of the study product(s).  
Considering the past 24 hours, please read each question and choose the answer that best reflects your experience with Robitussin use and your cough/cold:

1. Is your cough/cold making you less comfortable participating in social activities?
2. Is your cough making you self-conscious around people?
3. Are you worried about coughing in public?
4. Is your cough/cold making it more difficult for you to fall asleep?
5. Is your cough/cold making it more difficult to sleep through the night?
6. Is your cough/cold making you less energetic than usual?
7. Is your cough/cold making you less motivated than usual?

#### 14.2.2.2 Post treatment Questions (asked every day in the morning):

Considering the past 24 hours, please read each question and choose the answer that best reflects your experience with Robitussin use and your cough/cold:

1. After using Robitussin, is your cough/cold making you less comfortable participating in social activities?
2. After using Robitussin, is your cough making you self-conscious around people?
3. After using Robitussin, are you worried about coughing in public?
4. After using Robitussin, is your cough/cold making it more difficult to fall asleep?
5. After using Robitussin, is your cough/cold making it more difficult to sleep through the night?
6. After using Robitussin, is your cough/cold making you less energetic than usual?
7. After using Robitussin, is your cough/cold making you less motivated than usual?

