### 8.3.3 Secondary Endpoint Analysis(es)

For the secondary objective, measurements of health related QoL indicators will be evaluated using the specific QoL scores and categorized QoL scores change from baseline to each treatment day to determine the effectiveness of the two treatment groups (Daytime, Daytime+Nighttime).

Change from baseline in mean specific QoL scores and categorized QoL scores to each treatment day will be summarized and analyzed using a mixed-effects model for repeated measures (MMRM) with treatment, treatment day, as a discrete variable, and applicable baseline specific QoL scores or categorized QoL scores as fixed effect and a random intercept for each subject. Estimated marginal mean differences between baseline and each treatment day will be reported by treatment group including the mean difference on the original scale, standardized effect size including 95% confidence intervals (CI), and the respective p-value. The distribution of each outcome is assessed using Q-Q-plots by treatment group. In case of apparent deviations from the normal distribution, the changes from baseline are assessed using a Wilcoxon signed-rank test.

The QoL scores (sum of individual questions per category) will be categorized as below:

1. Sleep Quality
  - Sleep Well – WURSS-21 Q13
  - Falling asleep – QoL Q4
  - Sleep through the night – QoL Q5
2. Social Activities
  - Interact with others – WURSS-21 Q19
  - Less comfortable in social activities – QoL Q1
  - Self-conscious around others – QoL Q2
  - Coughing in public – QoL Q3
3. Physical Activities
  - Breathe easily - WURSS-21 Q14
  - Walk, climb stairs, exercise - WURSS-21 Q15
  - Accomplish daily activities - WURSS-21 Q16
4. Vitality
  - Energy – QoL Q6

- Motivation – QoL Q7
- Feel tired - WURSS-21 Q11

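### The specific QoL items are worded differently at baseline and at follow-up, so 10 of the 11 secondary change scores compare items that are not identical

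*Protocol*

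**What the plan says.** Protocol 14.2.2.1 lists seven questions to be answered before the first dose. None names a product within the item: the first is "Is your cough/cold making you less comfortable participating in social activities" and the third is "Are you worried about coughing in public". Protocol 14.2.2.2 lists the same seven for each morning of follow-up, all opening with a clause about having used Robitussin: "After using Robitussin, is your cough/cold making you less comfortable participating in social activities" and "After using Robitussin, are you worried about coughing in public".

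The lead-in is the same on both forms. It sets a 24-hour recall and tells the subject to "choose the answer that best reflects your experience with Robitussin use and your cough/cold". At baseline nobody has yet been sent the product, because Protocol 8.3 places the baseline questionnaires before shipment.

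Protocol 8.3.3 evaluates these data "using the specific QoL scores and categorized QoL scores change from baseline to each treatment day to determine the effectiveness of the two treatment groups". It then adds specific items to WURSS-21 items in four sums: "The QoL scores (sum of individual questions per category) will be categorized as below". SAP 4.6.1 gives the item scale as 0 to 7, lower being better.

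The study is open label (Protocol 7.3). Protocol 8.3 and SAP 1.2 analyse each group separately, with no comparison between groups. Neither document mentions the difference in wording, offers evidence that the two forms are equivalent or adjusts for it, and the limitations in Protocol 3.2 do not list it.

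**The concern.** A change score means something only if the same thing is measured twice. Here the follow-up item differs from the baseline item in three ways:

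- It names the sponsor's product inside the question, which can prompt the subject to think of the answer as a verdict on the product. For adverse events, Protocol 9.4 asks for non-leading questions; these items do not follow that principle.
- It presumes that the product was used.
- It may narrow the period rated. A subject can read the clause as the hours after a dose, although the lead-in says 24 hours. The baseline item carries no such restriction.

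The lead-in has a separate drafting fault. At baseline it asks about experience with a product not yet received, in subjects whom exclusion criterion 4 (Protocol 4.4) bars if they used such products in the previous 7 days.

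At stake is the reading of nearly all secondary results. Part of a reported improvement on these items could come from the change of question, and the planned analysis could not show how much.

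**Working it through.** **1. Items compared.** All seven follow-up items carry the product clause; no baseline item does. Item 4 also loses two words, without change of meaning. The recall period, lead-in and core content are otherwise the same.

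**2. Endpoints affected.** The composition of the sums is from Protocol 8.3.3 and SAP 4.6.2.

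| Secondary endpoint | Reworded components | Unchanged components |
|---|---|---|
| 7 single items | 1 of 1 each | none |
| Sleep Quality | 2 of 3 (items 4, 5) | WURSS-21 Q13 |
| Social Activities | 3 of 4 (items 1, 2, 3) | WURSS-21 Q19 |
| Vitality | 2 of 3 (items 6, 7) | WURSS-21 Q11 |
| Physical Activities | 0 of 3 | WURSS-21 Q14, Q15, Q16 |

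Affected: 7 + 3 = 10 of 7 + 4 = 11. The WURSS-21 has one printed form (Protocol 14.2.1), so the primary endpoints are untouched.

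**3. How a wording effect enters.** Let T0 and Td be the scores that the baseline wording would give at baseline and on day d, and b the average shift from the follow-up wording. The observed change is (Td + b) − T0 = (Td − T0) + b. For the sums, if each reworded item shifts by b, the change moves by 2b (Sleep Quality), 3b (Social Activities), 2b (Vitality) and 0 (Physical Activities).

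**4. What the model removes.** The baseline score is a covariate, but it was measured without b and so cannot absorb it. A constant b raises or lowers every Day 1 to Day 7 mean change alike. It cancels only in contrasts between follow-up days, or between groups given the same wording.

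**5. Sensitivity, for illustration only.** The plan has no figure on this point to reproduce. Protocol 8.1 plans 100 completers per group (200/(1 − 0.23) = 259.7, the stated 260 enrolled). The documents give no SD of change and no wording shift; both are assumed here. For a two-sided 5% within-group test with no true change, the chance of a nominally significant result is

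Φ(b√n/SD − 1.96) + Φ(−b√n/SD − 1.96), n = 100.

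| Assumed shift b (0–7 scale) | SD 1.5 | SD 2.0 | SD 2.5 |
|---|---|---|---|
| 0 (identical wording) | 5% | 5% | 5% |
| 0.25 | 39% | 24% | 17% |
| 0.50 | 92% | 71% | 52% |

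The smallest mean shift reaching p < 0.05 is 1.96 × SD/√100, that is 0.29, 0.39 and 0.49 for the three SDs. This cutoff applies to a mean change from any cause, so it says how sensitive the test is, not how large the wording effect is.

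**The case against.** The strongest reply is that nothing in the documents shows which way the wording pushes. A follow-up question asking whether, after use of the product, the cold makes sleep harder could even invite blame of the product. The lead-in names Robitussin on both forms, so the product is not newly mentioned at follow-up. Natural recovery, conceded in Protocol 3.2, already prevents causal attribution from these within-group changes. Only secondary endpoints are touched, SAP 4.6.1 calls the QoL analyses exploratory, and unchanged WURSS-21 items offer a partial benchmark.

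Much of this stands. A reader might infer that the items demonstrably lead subjects towards the product, or that the effect is about 0.3 to 0.5 points. The documents support neither: direction is unknown, and those figures are the generic test cutoff on assumed SDs.

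A reader might also infer that the follow-up form is often answered on days without product. The documents limit this. Protocol 5.5 ends the forms of early stoppers one day after the last dose, and a 24-hour recall may still cover that dose. SAP section 5 removes flagged diaries completed after reported stopping from all analysis tables. Some such days remain possible: Protocol section 10 keeps subjects discontinued early from product in the study, and SAP 4.5.1.1 computes change regardless of compliance. Their number is unknown.

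SAP 4.6.1 and 4.6.2 do mention between-group comparisons, in which a common wording effect would largely cancel. That conflicts with Protocol 8.3 and SAP 1.2 and would not repair the within-group changes.

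What the reply does not answer is that the items differ and are subtracted. The shared lead-in does not make them identical, and natural recovery is a separate source of confounding that the sponsor cannot remove, whereas this one it can.

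**Conclusion.** The point holds as a measurement fault in the secondary endpoints: 10 of 11 change scores rest wholly or partly on items whose wording changes between baseline and follow-up. With no control and no planned group comparison, any effect of the change enters the within-group estimate in full. That conclusion needs only the printed questions and the endpoint definitions.

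The size and direction are unknown. A shift towards the product is plausible because the clause names it in an open-label setting, but it is a possible bias, not a measured one. The percentages above depend on assumed SDs and shifts and on no true change. The finding does not reach the primary WURSS-21 endpoints or Physical Activities, leaves trends among follow-up days intact if the effect is constant, and does not justify dropping the prespecified analyses. It should be corrected or disclosed.

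**What to change.** If collection is still open, ask the baseline stems unchanged on every follow-up day, under a lead-in that asks only about the past 24 hours and names no product on either form. The cost is an ePRO text change with IRB notification. If the text changes during enrolment, subjects before and after will have different wording; flag them in the dataset.

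SAP section 5 describes diary problems that have already occurred, so the second route is the likelier one. If the data are already collected:

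- Keep the planned analyses.
- State in the SAP and the report that baseline and follow-up items differ in wording, and list this as a limitation.
- Do not attribute change on the reworded items to the product.
- Base the Sleep, Social and Vitality conclusions on WURSS-21 Q13, Q19 and Q11, whose wording is constant.

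Those three items are already single-item primary endpoints (Tables 14.2.1.5.1 and 14.2.1.4.1), so only SAP and report text is needed and no new analysis. The price is narrower content: one item stands in for a sum of three or four, and Q19, for instance, does not cover self-consciousness or worry about coughing in public.
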